8.6. Visit Windows

Study visits should take place within the time limits specified below:

D0 (first dose of vaccination) D1, D3, D7 (+/-1), D14 (+/-2), D30 (+/-7), D60 (+7) (second dose of vaccine), D61, D63, D67 (+/-1 from second vaccination), D74 (+/-2 from second vaccination), D90 (+/-7 from second vaccination), D180 (+/-14 from first vaccination, for each scheduled visit. An optional visit at any time point past 9 months (D270 +) from first vaccination may also take place.

This is also indicated on the Table of Events.

9. Mechanistic Assays

1. Expression of cytokines and chemokines via FACS. This assay will detect the expression profile of cytokines and chemokines to determine the innate response to vaccination.
2. Analysis of innate immune responses using FACS to assess numbers of activated innate cell populations. This assay will detect innate cell population activation including DC subsets, monocyte subsets, and NK cells, since these cell subsets are known to play crucial roles in immune regulation.
3. Molecular signatures of vaccination using RNA-seq on 2 mL of whole blood. This assay will determine the changes in mRNA and miRNA expression in whole blood. Results will be interpreted with use the method Significance Analysis of Microarrays (SAM) to determine change over baseline.
4. Microbiome Analysis: Analysis of microbiome diversity in the stool samples will be performed by Illumina MiSeq V4 16S Sequencing. Sample preparation will involve quantification and normalization of genomic DNA, PCR amplification of V4 hypervariable region of the bacterial 16S rDNA gene, PCR product quantification and library construction. Illumina MiSeq V4 16S sequencing and Bioinformatics analysis will involve V4 hypervariable region paired-end amplicon sequencing (MiSeq: 2x250 cycles). Filtering and trimming of all sequencing data will be done and mapped to taxonomic databases to identify bacterial composition in samples.
5. Levels of VZV-specific IgG/IgA/IgM antibody titers in the plasma by ELISA. This antibody assay will be used to quantify the levels of VZV-specific IgG and IgA in the plasma. Positive results will be assessed by 2X the negative control wells.
6. Number of VZV-specific IgG/IgA/IgM plasmablasts via ELISPOT. This cellular assay will be used to quantify the number of VZV-specific and total IgG/IgA/IgM antibody secreting cells in the blood. Positive results will be assessed by > 5 spots per million PBMCs.
7. Number of plasmablasts via flow cytometry. This cellular assay will be used to quantify the number of total plasmablasts in the blood.
8. Number of VZV-specific memory B cells in the blood via memory B cell assay. This cellular assay will be used to quantify the number of VZV-specific memory B cells in the blood. Positive results will be assessed by 2X the negative control wells.
9. In vitro stimulation and intracellular cytokine staining by flow cytometry. This cellular assay will be used to quantify the number of VZV-specific CD4 and CD8 T cells in the blood. Positive results will be assessed by either CD4+CD3+IFNg+CD40L+ or CD8+CD3+IFNg+CD40L+ after stimulation with VZV infected cell lysate or VZV-derived peptides.
10. Number of activated T cells in the blood via flow cytometry. This cellular assay will be used to quantify the number of VZV-specific CD4 and CD8 T cells in the blood using activation markers such as CD38, HLA-DR and Ki-67.

11. Phenotype of activated CD4 T cells in the blood via flow cytometry. This cellular assay will be used to characterize and quantify different CD4 T cell subsets.
12. Number and cross-reactivity of HLA-A2/IL1-specific CD8 T cells in the blood via flow cytometry. This cellular assay will be used to quantify the number and characterize the cross-reactivity of HLA-A2/IL1-specific CD8 T cells in the blood using MHC-I tetramer staining.
13. Flow cytometric sorting of blood plasmablasts and cloning of immunoglobulins to generate monoclonal antibodies. This cellular assay will be used to generate VZV-specific monoclonal antibodies to assess their avidity and protective capacity as well as the overall breadth of the immunoglobulin repertoire.

10. Biospecimen Storage

1. Plasma will be collected from CPT tubes, aliquoted in sterile 1.5 ml microcentrifuge tubes and placed in a -20°C freezer that is monitored by an electronic monitoring alarm that makes a loud noise if the temperature is warmer than -10°C. The freezer temperature is monitored daily.
2. PBMCs will be collected from CPT tubes, cryopreserved and placed in an automatic fill liquid nitrogen freezer. This freezer has an audible alarm if the liquid nitrogen level or temperature is low. The freezer temperature is monitored daily.
3. Stool will be aliquoted from the specimen collection container into new cryovials and will be placed in a -80°C freezer that is monitored by an electronic monitoring alarm that makes a loud noise if the temperature is warmer than -60°C. The freezer temperature is monitored daily.

11. Criteria for Participant and Study Completion and Premature Study Termination

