Exploratory Endpoint(s)/Outcome(s)	
The changes in transcriptomics, metabolomics and immune cell populations between D0 (before vaccination) and D1, D3, D7, D14 and D30 after each dose of Zoster vaccine recombinant, adjuvanted, in both age groups.The changes in the phenotype of T cell responses and the kinetics of these changes between D0 (before vaccination) and D7, D14 and D30 after each dose of Zoster vaccine recombinant, adjuvanted, as well as D180 and D270+ (optional visit) in both age groups.The changes in the magnitude of activated B cells, antibody secreting cells and memory B cells and the kinetics of these changes between D0 (before vaccination) and D7, D14 and D30 after each dose of Zoster vaccine recombinant, adjuvanted, as well as D180 and D270+ (optional visit) in both age groups.The changes in VZV serology between D0 (before vaccination) and D14 and D30 after each dose of Zoster vaccine recombinant, adjuvanted, as well as D180 and D270+ (optional visit) in both age groups.The changes in specificity, magnitude and phenotype of VZV-specific (gE and other antigens) T cells and the kinetics of these changes between D0 (before vaccination) and 7, 14, 30 days after each dose of Zoster vaccine recombinant, adjuvanted, and at D180 and D270+ (optional visit) in both age groups.The changes in magnitude of VZV-specific B cells and the kinetics of these changes between D0 (before vaccination) and 7, 14, 30 days after each dose of Zoster vaccine recombinant, adjuvanted, and at D180 and D270+ (optional visit) in both age groups.

	
 • The collection of stool at baseline for microbiome analysis
Accrual Objective	
N=60 subjects receiving 2 doses of Zoster vaccine recombinant, adjuvanted separated by 60 days including:
 
 • N=30 subjects between the ages of 50-60 years. • N=30 subjects age 70 years and above.
Study Duration	24 - 27 months (18 months accrual + 9 months of study participation, with an optional visit at 9 months and beyond after the first vaccination).
Treatment Description	Not applicable
Inclusion Criteria	
 1. Subject must be able to understand and provide informed consent. 2. Adults aged 50-60 years, or community dwelling adults aged 70 years and above.

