8.1. Enrollment

The research study will be explained in lay terms to each potential research participant. The potential participant will sign an informed consent form before undergoing any study procedures. Once the informed consent has been signed, the participant is considered enrolled in the study and will be assigned a unique participant number.

Enrollment will be completed within 18 months. The duration of participation for each subject is 6 months, with an optional visit at 9 months and beyond after the first visit.

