13.4.5 Analyses of Exploratory Endpoint(s)/Outcome(s)

Exploratory Endpoint 1. The innate immune response signatures are identified from traditional immune parameters, gene expression measured by RNA-seq experiment, and metabolomics data measured by LC/MS. The innate signatures will be identified for the two age groups separately. The traditional immune parameters, genes, and metabolites that change significantly over baseline after immunization are considered innate signatures.

Traditional markers will be tested using paired t-test or Wilcoxon test against D0, and significant markers will be considered part of the innate immune signature.

RNA-seq data will be preprocessed using Bowtie and Tophat, and FPKM (fragments per kilobase of exon model per million mapped reads) values will be calculated. Gene level comparison of D1, D4, D14 and D30 vs D0 will be conducted using DESeq to find the transcriptomics signature of vaccination.

Metabolomics data will be processed using packages apLCMS, XCMS, and xMSAnalyzer and generate data tables containing accurate mass m/z , retention time(s), intensity, coefficient of variation, and

related descriptive characteristics, including minimal information standards for metabolomics data. SAM(8) and similar methods will be used to detect differential abundance of features between D1, D4, D14 and D30 vs D0 to select metabolic innate signatures.

After each vaccination, the innate signatures that are correlated with the D30 antibody titers are considered correlation signatures of the innate immune responses. The correlation will be assessed using Spearman's correlation and the associated p-values.

Exploratory Endpoint 2. We will use paired t-test or Wilcoxon test to compare each immune parameter (changes in phenotype of T cell responses and the kinetics of these changes) between D7, D14 and D30 after vaccination and D0 for each dose of Zoster vaccine.

Exploratory Endpoint 3. We will use paired t-test or Wilcoxon test to compare each immune parameter (changes in the magnitude of activated B cells, antibody secreting cells and memory B cells and the kinetics of these changes) between D7, D14 and D30 after vaccination and D0 for each dose of Zoster vaccine.

Exploratory Endpoint 4. We will use paired t-test or Wilcoxon test to compare VZV serology between D14, D30, D180 and D270+ (optional visit) after vaccination and D0 for each dose of Zoster vaccine.

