Exploratory Endpoint 5. We will use paired t-test or Wilcoxon test to compare each immune parameter (changes in specificity, magnitude, and phenotype of VZV-specific T cells and the kinetics of these changes) between D7, D14, D30, D180 and D270+ (optional visit) after vaccination and D0 for each dose of Zoster vaccine.

Exploratory Endpoint 6. We will use paired t-test or Wilcoxon test to compare each immune parameter (changes in magnitude of VZV-specific B cells and the kinetics of these changes) between D7, D14, D30, D180 and D270+ (optional visit) after vaccination and D0 for each dose of Zoster vaccine.

Although our statistical methods will adhere to what is proposed herein, our experience with analyses of similar studies in the past has underscored the need for flexibility and adaptability in trying different statistical approaches to arrive at the most informative results. As such, we may use alternative approaches such as the gene set enrichment analyses, or other approaches, in an *ad hoc* basis.

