APPENDIX D. SCHEDULE OF EVENTS

Day	D -28 - D0	D0	D1	D3	D7 +/- 1	D14 +/- 2	D3 0 +/- 7	D60 + 7	D61	D63	D67 +/- 1*	D74 +/- 2*	D90 +/- 7*	D18 0+/- 14**	D27 0+** ***
Visit	Screen -ing	1	2	3	4	5	6	7	8	9	10	11	12	13	14
Informed Consent & HIPPA***	X														
Verify Eligibility Criteria	X	X						X							
PID assignment	X														
Demographic and Medical History (including medication and vaccine history).	X	X	X	X	X	X	X	X	X	X	X	X	X	X	X
Concomitant Medications	X%	X%	X	X	X	X	X	X	X	X	X	X	X	X	X
Vital signs (Oral Temperature, Pulse Rate, and BP)	X	X	(X)	(X)	(X)	(X)	(X)	X	(X)	(X)	(X)	(X)	(X)	(X)	(X)
Height and Weight	X														
Focused physical exam (only if indicated based on review of health status)	X	X	X	X	X	X	X	X	X	X	X	X	X	X	X
Vaccination		X						X							
Assessment of health status 15 minutes after administration of study vaccine		X						X							
Memory Aid Review			X	X	X				X	X	X				
Instruction given to study subjects on safety events and concomitant medications****		X	X	X	X	X	X	X	X	X	X	X	X	X	
Blood draw for Innate Assays and Adaptive Assays		X	X	X	X	X	X	X	X	X	X	X	X	X	X
Stool collection	X	X													
Adverse Events		X	X	X	X	X	X		X	X	X	X	X	X	
Serious Adverse Events		X	X	X	X	X	X	X	X	X	X	X	X	X	X

Footnotes:

%All current medications and medications taken within 30 days prior to day 0 of the study.

* Windows here are in relation to the second (D60) vaccination: D67 (+/-1 from second vaccination), D74 (+/-2 from second vaccination) and D90 (+/-7 from second vaccination).

** D180 +/- 14 days from first vaccination,

***Prior to study procedures

*****D270+, an optional visit at 9 months and beyond, after the first visit may occur.

Any Adverse Event (including – but not limited to- vaccine reactions and local or systemic reactogenicity events) of grade 2 or higher severity or serious adverse event (SAE) occurring after vaccination while the subject is still at the clinical site will be recorded and reported.

**** Instruction includes the following:

1. Subjects will be provided (on D0 and D60 only) with a written description of local and systemic vaccine reactions of mild, moderate and severe intensity and instructed to call the site to report reactogenicity events of grade 3 severity within 1 week following vaccination.

2. Subjects will also be instructed to promptly call the site if he/she develops any of the following:

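### The optional D270+ visit has no upper time limit but is tested as one time point in exploratory endpoints 4-6, so it cannot describe late kinetics or age differences without using actual time since dose

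*Combined protocol and SAP*

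**What the plan says.** The visit has a lower limit only. Section 8.6 states "An optional visit at any time point past 9 months (D270 +) from first vaccination may also take place", and the schedule of events in Appendix D gives it one column with the footnote "D270+, an optional visit at 9 months and beyond, after the first visit may occur". By contrast, D180 has a window of 14 days either side.

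Section 13.4.5 uses the visit as a single time point, by paired t-test or Wilcoxon test. For endpoint 4 the plan is to "compare VZV serology between D14, D30, D180 and D270+ (optional visit) after vaccination and D0 for each dose of Zoster vaccine". For endpoints 5 and 6 (VZV-specific T and B cells) the comparison is "between D7, D14, D30, D180 and D270+ (optional visit) after vaccination and D0 for each dose of Zoster vaccine". Endpoints 2 and 3 also name D180 and D270+ in their definitions (sections 3.4 and 13.2), but their planned tests cover only the contrasts "between D7, D14 and D30 after vaccination and D0 for each dose of Zoster vaccine".

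The timeline comes from two places. The synopsis gives a study duration of "24 - 27 months (18 months accrual + 9 months of study participation", with the optional visit included. Section 8.1 says "Enrollment will be completed within 18 months" and "The duration of participation for each subject is 6 months, with an optional visit at 9 months and beyond after the first visit".

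No section sets an analysis window for D270+ or uses actual time since dose. Section 13.4.1 asks only for D0 and D30 measurements. The missing-data methods in section 13.4 cover cytokine, gene expression and metabolomics data, not serology or the T- and B-cell assays.

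**The concern.** D270+ is the only sample planned beyond about six months, so any statement about late persistence depends on it. Section 2.4 makes the kinetics of VZV-specific T and B cells, and age differences in them, exploratory objectives. Section 13.4.6 plans a visual comparison of log2 titres by group at each time point.

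A D270+ summary pools samples that may be more than a year apart, from people who chose to come back. How late someone can be sampled depends on when they enrolled. If the two age cohorts enrolled at different rates or returned at different times, a difference in sampling time could look like an age difference in persistence. Selective return could do the same.

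**Working it through.** **1. Reproduce the stated duration.** Inputs: accrual of 18 months (synopsis, section 8.1); participation of 6 months (section 8.1), or 9 months with the optional visit (synopsis).

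- 18 + 6 = 24 months and 18 + 9 = 27 months, which matches the stated 24-27.

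**2. Possible time since dose 1 at D270+.** For a participant enrolled at month e in a study that closes at month C, the earliest time is 9 months and the latest is C − e.

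| Enrolled at month | C = 27 | C = 24 |
|---|---|---|
| 0 | 9 to 27 | 9 to 24 |
| 9 | 9 to 18 | 9 to 15 |
| 15 | 9 to 12 | 9 only |
| 18 | 9 only | not reachable (24 − 18 = 6) |

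The widest span is 27 − 9 = 18 months, or 24 − 9 = 15 months, against 28 days at D180. These upper limits are inferred from the study duration; section 8.6 itself sets none.

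**3. A less extreme picture.** Assume uniform accrual over 18 months, closure at month 27, and a visit time uniform over what each person's timeline allows. Simulation then gives a mean of 13.5 months, an SD of 4.0, and a 5th-95th percentile range of 9.2-21.6 months. The documents do not give these distributions.

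**4. What the spread could do to the response.** Assume log-linear decay with half-life h months. Two samples t months apart then differ by a factor of 2^(t/h). The documents give no half-life, so a range is shown.

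| Half-life (months) | 9 vs 27: 2^(18/h) | 9 vs 24: 2^(15/h) | 9.2 vs 21.6: 2^(12.4/h) |
|---|---|---|---|
| 6 | 8.0 | 5.7 | 4.2 |
| 12 | 2.8 | 2.4 | 2.0 |
| 24 | 1.7 | 1.5 | 1.4 |

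With a half-life of 48 months, 9 versus 27 months still gives 2^(18/48) = 1.3.

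**5. Time since dose 2.** D270+ is timed from dose 1, while section 8.5 allows a second dose missed because of COVID-19 to be given later. Time since the last dose can therefore vary even among people seen on the same study day.

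**The case against.** The strongest reply is that little depends on this visit. It is optional and exploratory, and it plays no part in the primary analysis (section 13.4.2), the safety analysis (13.4.4) or the sample size (13.7). Each attender is compared with their own D0, so the test validly detects any change in attenders. Section 13.4 specifies no D270+ versus D90 or D180 test, and its only between-group test is Fisher's exact test for adverse events. All of that stands. It limits the point to how D270+ is interpreted, but does not remove it, because the kinetics and age objectives still need a defined time scale. The allowance in section 13.4.5 for alternative methods as the need arises does not supply one.

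Three stronger readings are tempting, and the documents do not support them:

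- **That the paired test is invalid.** It is not; what is lost is the meaning of D270+ as a defined time.
- **That an eightfold distortion is to be expected.** It needs a participant enrolled at the start and seen at month 27, another seen at month 9, and an assumed 6-month half-life throughout.
- **That the plan attempts a dose-specific contrast at D270+, because section 13.4.5 describes the tests for each dose.** The endpoint definitions in sections 3.4 and 13.2 attach the per-dose wording to the early samples and list D180 and D270+ separately. The loose phrasing in 13.4.5 applies equally to D180.

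**Conclusion.** The point holds for exploratory endpoints 4-6. As planned, D270+ versus D0 shows whether attenders changed, but its mean mixes waning with enrolment date and choice to return. It cannot support the late-kinetics or age-cohort objectives as a defined time point.

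Time since dose 1 may range from about 9 months to a worst case of 24-27 months. The fold differences of 8.0, 2.8 and 1.7 (9 versus 27 months), or 5.7, 2.4 and 1.5 (9 versus 24 months), rest on assumed half-lives of 6, 12 and 24 months and show sensitivity only. The actual effect depends on attendance, visit dates and decay, none of which the documents give. This is a cheap improvement, not a threat to the study's main conclusions.

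**What to change.** - Keep D270+ versus D0 as a descriptive test in attenders, labelled as such.
- Base late kinetics on a mixed model with a participant effect, age cohort and actual days since the second dose, using post-dose-2 samples (D90, D180, D270+) from participants who received both doses. A cohort-by-time term would address age differences in decline. Where the second dose was late, a D180 sample taken before it does not enter.
- Summarise one-dose participants separately. Section 13.4.1 admits them to the analysis population, and they should not share a decline curve with two-dose participants.
- Use log2 for antibody titres, as in section 13.4.6, and a suitable transformation for cell counts that may include zeros.
- Report D270+ attendance and the range of days since each dose by cohort, and compare D180 values of attenders and non-attenders.
- In the same edit, reconcile the definitions of endpoints 2 and 3, which include D180 and D270+, with planned tests that stop at D30.

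No extra visit or sample is needed, since visit and dose dates supply the time variable. The cost is a little more analysis work and an assumption about the shape of decline, which should be stated and checked against the data.

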11.1. Participant Completion

Efforts are made to encourage participants to attend all clinic visits. To achieve the primary end points of the study, we will need to have longitudinal data on participants who should be able to complete, within the required windows, at least the following visits: D1, D3 and D30 after vaccination. The minimum amount of blood needed on the critical visits stated above to fulfill the primary endpoints is: 1 CPT tube.

11.2. Participant Stopping Rules and Withdrawal Criteria

Participants may be prematurely terminated from the study for the following reasons:

1. The participant elects to withdraw consent from all future study activities, including follow-up.
2. The participant is “lost to follow-up” (i.e., no further follow-up is possible because attempts to reestablish contact with the participant have failed).
3. The participant dies.
4. The Investigator no longer believes participation is in the best interest of the participant or that the study procedures, if conducted, risk compromising the scientific integrity of the study.

11.3. Participant Replacement

Participants who withdraw or are withdrawn will not be replaced if they have received at least one dose of the study vaccination.

11.4. Follow-up after Early Study Withdrawal

If a participant is withdrawn from the study for any reason, the participant may be asked to complete a final visit and/or final assessments. At this visit, study personnel may review the memory aid with the subject (if within 7 days of vaccination) review the vaccination site, list of medications, and note any other AEs or SAEs since last visit. Blood may be drawn. Physical examination will be performed only if indicated, based on review of health status. Subjects will be also asked to report local and systemic AEs and any blood draw-related AEs. These visits will last about 1 hour.

11.5. Study Stopping Rules

The study may be prematurely terminated for the following reasons:

- If Shingrix® is recalled by the manufacturer

The study will be placed on hold (for both enrollment and vaccine dosing) for expedited ISM review for the following reasons:

- A death of a participant, which is possibly or definitely related to the study vaccine
- The occurrence of one study vaccine-related and unexpected SAE or Grade 4 AE

12. Assessment of Safety

